The attending proceduralist will perform the SGB in the ICU/progressive care. ICU/progressive care nurse will provide patient monitoring and assistance during the procedure. Standard monitors and ACLS resuscitative equipment will be immediately available. A norepinephrine solution will be at bedside to treat potential hypotension associated with SGB. The SGB perineural catheter will be placed using standard sterile technique. Initial perineural bolus injection - clonidine 100 mcg, Decadron PF 5mg, and 0.25% bupivacaine 5 ml is delivered. A Cadd perineural infusion 0.2% bupivacaine will be initiated at 2ml/hr for 5 days. Acute pain service will discontinue infusion and remove the catheter after 5 days.

All adverse events and serious adverse events related to the SGB. All other adverse and serious adverse events, including death will be reported per IRB requirements. Laboratory analysis will be obtained at baseline (prior to block, baseline) and on day 1, day 3, and day 5. Labs include a cytokine panel (TNF-beta, IL-6, and IL-1 β), measurements of exhaled nitric oxide levels, and CRP (daily). Vital Parameter Analysis: Oxygenation, supplemental oxygen, type of respiratory support and need for mechanical ventilation, blood pressure i.e. hypotension requiring vasopressors and utilization of ECMO, heart rate, heart rhythm/new dysrhythmias, ICU/progressive care length of stay and discharge disposition will be collected from the EMR.

Control group: There will be no sham procedure for the control group. The control group will have nitric oxide levels performed once a day by a member of the research team. Lab draws will be drawn at the same frequency as the treatment group.

Treatment group:

The treatment group will have a SGB placed by the APS.

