- b) Differences in mean/median values for SGB vs SOC will be assessed at treatment day 5 - adjusted for baseline levels
- c) Differences in changes from baseline levels for SGB vs SOC as measured by comparison in slope trends;
- d) Differences in frequency of adverse events for SGB vs SOC over the study period from treatment through 90 day of follow up;

Secondarily,

- e) Differences between SGB vs SOC in *frequency and time to occurrence of cardiac arrhythmias*;
- f) Differences between SGB vs SOC in frequency of *need for and duration of use mechanical ventilation and/or extracorporeal membrane oxygenation (ECMO)*;
- g) Differences between SGB vs SOC in survival experience over treatment period through 90 -day discharge follow up

Sample Size issues:

For power computations we assume that SGB will particularly have an impact in reduction of inflammatory response as measured by IL-6. Looking at a meta-analyses of IL-6 values [Ulhaq ZS, Soraya GV. Interleukin-6 as a potential biomarker of COVID-19 progression. *Med Mal Infect.* 2020;50:382–383. doi: 10.1016/j.medmal.2020.04.002. 2020/04/08] and picking the largest of studies of COVID patients [Qin C, Zhou L, Hu Z, Zhang S, Yang S, Tao Y, et al. Dysregulation of immune response in patients with COVID-19 in Wuhan, China. *Clin Infect Dis* 2020, <http://dx.doi.org/10.1093/cid/ciaa248> [pii: ciaa248].], we estimate the overall mean (SD) IL-6 for COVID-19 patients to be 21 pg/mL (30.1). Using these estimates we see that a sample of 16 patients equally randomized into SGB (n=8) and SoC (n=8) would provide sufficient power to observe magnitude of differences in mean of IL-6 from as small as about 50 pg/mL and larger with 80% power at the 5% significance level assuming 2-sided hypothesis testing. (see Power Figure). The study [Liu MH, Tian J, Su YP, Wang T, Xiang Q, Wen L. Cervical sympathetic block regulates early systemic inflammatory response in severe trauma patients. *Med Sci Monitor.* 2013;19:194–201.], indicates that SGB is capable of eliciting reductions of IL-6 between groups and from baseline of magnitudes of greater than 100 pg/mL within 72hrs of first injection.

Section 7.0 Study Parameters:

Baseline Assessments

- Current Fio₂/PaO₂ ratio
- Current type of ventilation and oxygen use
- Current production of nitric oxide via Niox
- Current blood pressure and heart rate parameters
- Labs: IL-1beta, TNF-alpha, IL-6, ABG, CRP
- Chest x-ray
- Need for mechanical ventilation or other support

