Initial perineural bolus injection will include clonidine 100 mcg, decadron PF 5mg, and 0.25% bupivacaine 5 ml.

Perineural catheter:

Infusion of 0.2% bupivacaine will be initiated at 2ml/hr for 5 days.

All medications are FDA approved. Standard orders for perineural blocks will be entered into the EMR system. Pharmacy responsible for ICU/progressive care will dispense orders for the medication used in the SGB. Pharmacist in ICU/progressive care will fill Cadd pump infusion catheter once per day per standard procedure in the ICU/progressive care.

Section 9.0 Adverse Event Reporting Guidelines:

The initial procedure will be stopped and the patient will be withdrawn if any of the following occurs; vasopressor or unresponsive hypotension, intrathecal injection, pneumothorax, expanding hematoma, allergic reaction, or cardiac arrhythmias. For continuous infusions, the catheter will be removed and the patient will be withdrawn if any of the following occur: local systemic toxicity, seizure, catheter migration to intravascular or intrathecal space, expanding hematoma, vasopressor unresponsive hypotension, symptomatic bradycardia, insertion site infection. Any adverse events will be treated with Nebraska Medicine standard of care procedures. Subjects can also voluntarily withdraw at any time. The PI can also withdraw any subject that is not felt to be a suitable candidate for the study.

Serious adverse events directly related to block will result in withdrawal. Directly block related serious adverse events include: local systemic toxicity, seizure, serious allergic reaction, expanding hematoma, or catheter migration to intravascular or intrathecal space, insertion site infection. As well, patients will be withdrawn if the patient develops medication unresponsive bradycardia or hypotension. This may not be directly related to block but discontinuation of infusion may facilitate resuscitation of patient. Expected complications may include voice hoarseness, ipsilateral eyelid drooping, mild pain at site of catheter, and blurred vision. Occurrence of expected complications will not result in withdrawal from study unless demanded by the patient.

Section 10.0 Statistical Considerations:

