Statistical considerations for primary objective, the analysis would include means/medians (standard errors, IQRs) at each time point - and also represented by error bars - and comparisons using t test or the Mann-Whitney U test as appropriate. Multivariate analyses using Generalized estimating equations (GEE) and to compare longitudinal changes in the two groups adjusting for confounders and as well as ANCOVA based regression to measure before and after changes. Kaplan-Meier survival methods to measure time to defined thresholds and Cox regression to assess any impact of confounders.

For safety - AE's will be assessed by providing descriptive statistics related to their frequency (summarized by occurrence, percentage of occurrence, severity, seriousness, outcome, relation to treatment, start time summary, duration of AE analysis) as well as graphically via box plots and cumulative incidence plots indicative of distributions in the two trial groups. Non-parametric methods (e.g. Fisher Exact testing) will be used to statistically compare the period frequency of events between the two groups. In general, timely analysis, by creating summaries of adverse events and other safety measurements such as relevant vital signs, ECG, Laboratory abnormal findings will be done to keep a check on the increase in intensity of observations taken at baseline and/or new findings arisen after baseline.

Secondary measures:

Occurrence of cardiac arrhythmias, need for mechanical ventilation and/or ECMO as well as overall survival will be compared using time-to-event based methods (e.g. Kaplan-meier curves). The expectation is that any non-statistically significant but implied trends will be evaluated in larger phase IIb /III trial that will follow.

Stopping Rules:

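### Section 9.0 withdraws patients from the study for harms only the SGB arm can have, with no follow-up or analysis rule, so the Day 90 safety and survival comparisons risk one-sided informative loss

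*Combined protocol and SAP*

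**What the plan says.** Section 9.0 sets three withdrawal rules tied to the block.

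- During placement: "The initial procedure will be stopped and the patient will be withdrawn if any of the following occurs". Cardiac arrhythmia is among the listed events.
- During the infusion: "the catheter will be removed and the patient will be withdrawn if any of the following occur".
- For block-related serious events: "Serious adverse events directly related to block will result in withdrawal".

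The same section then describes the contrasting case: "Occurrence of expected complications will not result in withdrawal from study unless demanded by the patient". It also allows voluntary withdrawal, withdrawal by the investigator, and withdrawal for bradycardia or hypotension that does not respond to medication. Those three are not worded by arm.

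For controls, Section 5.0 says "There will be no sham procedure for the control group".

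The comparisons affected are in Section 6.0. Item (d) is "Differences in frequency of adverse events for SGB vs SOC over the study period from treatment through 90 day of follow up", and item (g) is "Differences between SGB vs SOC in survival experience over treatment period through 90 -day discharge follow up". Section 10.0 compares adverse event frequencies by Fisher's exact test and states that "overall survival will be compared using time-to-event based methods (e.g. Kaplan-meier curves" will be used.

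No section defines an analysis population, an as-randomised analysis, a censoring rule, the handling of missing data, or data collection after withdrawal.

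**The concern.** Each of the first two rules orders two actions: stop the procedure or remove the catheter, and also withdraw the patient. Followed as written, an SGB patient harmed by the block leaves the trial, while no control can leave under these three rules. A control who has an arrhythmia or a seizure stays in. An SGB patient who has an arrhythmia during placement, or a seizure during the infusion, does not.

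Safety and tolerance lead the objectives in Section 1.0. The plan could lose the later adverse events, the remaining Day 1 to Day 5 biomarkers and the 90-day survival of the patients who tell most about harm. If withdrawals are censored, Kaplan-Meier estimation treats that censoring as unrelated to prognosis, although harm caused it. Arrhythmia is affected in particular: it is a withdrawal trigger, a secondary outcome (Section 6.0, item e) and a route of entry (Section 3.0).

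**Working it through.** **1. Does withdrawn mean leaving the study?** The term is not defined. Three features of Section 9.0 favour that reading. The two-action sentences would be redundant if it meant only stopping treatment. The sentence on expected complications speaks of withdrawal from the study. The investigator's power to withdraw concerns suitability for the study. One sentence points the other way: stopping the infusion may help resuscitation. It explains only the rule on unresponsive bradycardia or hypotension.

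**2. Which triggers act on one arm only?** The placement, infusion and block-related rules presuppose a block, and controls have none. The other withdrawal routes could apply to either arm and are left out of this point.

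**3. The plan's own figure, and whether power suffers.** Inputs from Section 6.0: SD 30.1 pg/mL, 8 per arm, two-sided 5%, 80% power, detectable IL-6 difference about 50 pg/mL. For a two-sample t test the noncentrality is d / [SD × √(1/n1 + 1/n2)] with n1 + n2 − 2 degrees of freedom. At 8 vs 8 and d = 50 this is 50 / (30.1 × 0.5) = 3.32 on 14 df, which gives 87% power. The difference detectable with 80% power is 45.3 pg/mL. For a Mann-Whitney test at its worst-case efficiency of 0.864 it is 49.5 pg/mL, which agrees with the stated figure.

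| SGB vs control | Detectable at 80% power (t test) | Power at 50 pg/mL |
|---|---|---|
| 8 vs 8 | 45.3 | 87% |
| 7 vs 8 | 47.2 | 84% |
| 6 vs 8 | 49.6 | 81% |

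Losing one or two SGB patients keeps the detectable difference within about 50 pg/mL. The problem is bias, not power.

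**4. How likely is a loss?** No withdrawal rate is given. The 10% SAE/ADR background rate in Section 10.0 is borrowed as an illustration; 5% and 20% are assumed. P(at least 1 of 8) = 1 − (1 − p)^8, and P(at least 2 of 8) = 1 − (1 − p)^8 − 8p(1 − p)^7.

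| p | At least 1 | At least 2 |
|---|---|---|
| 5% (assumed) | 34% | 6% |
| 10% (borrowed) | 57% | 19% |
| 20% (assumed) | 83% | 50% |

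Each loss is 1/8 = 12.5% of the arm.

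**5. What one loss does to survival.** Assume 3 true SGB deaths: 3/8 = 37.5%. One patient is withdrawn before the first death, with vital status unknown.

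- The withdrawn patient dies unseen: the Kaplan-Meier estimate is 1 − (6/7)(5/6) = 2/7 = 28.6%, or 8.9 points too low.
- The withdrawn patient survives: 3/7 = 42.9%, or 5.4 points too high.

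In expectation the bias is w × (mortality of retained − mortality of withdrawn). With w = 1/8 and assumed mortality of 30% and 60%, this is 0.125 × (0.30 − 0.60) = −3.75 points. With equal mortality it is zero.

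**6. What it does to adverse events.** The triggering event precedes withdrawal, so it can be counted, and a recorded procedural arrhythmia counts against SGB. The events at risk of being missed are those after withdrawal.

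**The case against.** The strongest reply is that silence is being read as absence. The plan never says that data collection ends at withdrawal. Section 5.0 has other adverse events and deaths reported under IRB requirements and takes many outcomes from the electronic record. Section 10.0 reports the outcome and duration of adverse events, which implies following the triggering event past its onset. The consent form may say more, but it is not among the documents reviewed. These points reduce the likely loss. None of them keeps a withdrawn patient in the Day 1 to Day 5 sampling, the Day 90 call or the analysis.

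Several narrower points stand:

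- The stopping table in Section 10.0 counts events against subjects enrolled. A withdrawn patient therefore stays in that calculation, and the main safety boundary is not weakened by losing the patient afterwards.
- Vasopressor-unresponsive hypotension in the infusion list overlaps the rule on unresponsive hypotension that is not worded by arm. That one trigger is not clearly exclusive to SGB.
- The withdrawal and mortality figures used here are illustrations, not estimates from the documents.
- Survival is secondary. With 8 per arm, a two-sided Fisher test needs a split such as 0 vs 5 deaths for p = 0.026; 0 vs 4 gives p = 0.077. A shift of a few points will not change a significance statement.

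The last point does not remove the concern. Section 10.0 intends to carry non-significant trends into a larger trial, so the point estimates and the safety description are what this study delivers.

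**Conclusion.** The concern holds. Section 9.0, on its more natural reading, removes patients from the study for placement, catheter and block-related harms that arise only in the SGB arm, and nothing in the plan recovers their later data or fixes how they are analysed. The chance of at least one such loss is 57% if the withdrawal rate equals the borrowed 10%, and 34% to 83% over assumed rates of 5% to 20%. In the assumed 3-of-8 example, one loss moves the SGB mortality estimate by −8.9 or +5.4 points. Bias in favour of SGB is likely, because harm causes the withdrawal, but it is not certain: it depends on the prognosis of those withdrawn and vanishes if that equals the prognosis of the others. IL-6 power is not the issue. The point should be fixed. If only treatment discontinuation was intended, the text should say so, and the same wording change settles it.

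**What to change.** Leave the clinical criteria for stopping the procedure or infusion as they are, and change only what happens to the patient's data.

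1. In Section 9.0, replace withdrawal of the patient with discontinuation of study treatment, and state that the patient remains in the study. Define withdrawal from the study as withdrawal of consent to follow-up.
2. Continue scheduled labs, vital signs, adverse event collection and the Day 90 call for every randomised patient unless consent is withdrawn. Apply this also to patients the investigator withdraws; discretion over treatment need not change.
3. In Section 10.0, analyse every patient in the randomised arm. Count the triggering event as an adverse event and, where it is an arrhythmia, as an arrhythmia endpoint event.
4. State that survival is censored only at last known contact or withdrawal of consent. Report best-case and worst-case bounds where vital status is unknown.
5. Report treatment discontinuations by arm, with numbers and reasons.

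The cost is an amendment, with consent wording if needed. For each patient who discontinues there is also the staff time and sampling for the remaining Day 1 to Day 5 cytokine, CRP and exhaled nitric oxide measurements. These, the electronic-record data and the Day 90 call are already scheduled for every randomised patient.

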Available research indicates that an exaggerated immune response plays a key role in the cardiopulmonary pathophysiology of COVID-19. Preliminary data from previous studies at UNMC suggest that acute lung injury initiates robust and sustained macrophage activation in thoracic dorsal root ganglia and in stellate ganglia, resulting in increased cardiac and pulmonary afferent and efferent neuronal sensitivity. In the current proposal, we plan to validate a novel therapeutic strategy to treat coronavirus-induced cardiopulmonary symptoms and complications by local delivery of bupivacaine, dexamethasone, and clonidine to the stellate ganglia. Single injection and continuous infusion SGB have been safely utilized clinically and in many human studies.

Section 3.0 Eligibility Criteria:

Inclusion:

- Subject admitted to COVID ICU/progressive care, age 40-75 years old

Subjects must have + covid test with signs of impending respiratory compromise as identified by having at least 2 of the following:

- Respiratory rate ≥ 30 breaths per min
- Oxygen saturation at rest $\leq 93\%$
- $\text{PaO}_2/\text{FIO}_2 \leq 200$ mm Hg
- bilateral infiltrates on chest radiograph or CT not due to cardiac failure
- Requiring non-invasive or invasive mechanical ventilation.

Any patient with a + covid test and any cardiac tachydysrhythmia (excluding sinus tachycardia) will be included regardless of respiratory status. (Note: The broader inclusion of patients who have cardiac tachydysrhythmia is based on our prior experience and other reported beneficial antiarrhythmic effects of SGB in this patient group.)

Exclusion:

- Hemodynamic instability (>2 vasopressors)
- Heart rate < 60 beats per minute
- Systolic Blood pressure of less than 80 mmHg
- pre-hospital diagnosis of heart failure or fluid overload
- anatomical inability to perform block
- prior sympathectomy
- Patient currently enrolled in another clinical trial for COVID-19 or respiratory distress/ARDS
- Uncorrectable coagulopathy
- ECMO already engaged
- On Nitric Oxide
- Pre-existing multi-organ failure (>2 organ systems)
- Allergic to dexamethasone, clonidine, or bupivacaine.
- If female, currently pregnant or breast-feeding.
- Investigators determine the subject would be too unstable to participate in the study intervention.

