If a woman of childbearing age is enrolled as a subject and there has not been a pregnancy test during their current inpatient stay, a urine or blood pregnancy test will be performed. Pregnancy will not be allowed for this study as the drug is absorbed systemically and there are known risks to the fetus.

Section 4.0 Registration Procedure:

A prospective block randomized phase I/II two arm unblinded trial of a modified SGB protocol incorporated into Standard of Care vs UNMC standard of care Only for ARDS COVID-19 patients.

Subjects and/or Legally Authorize Representative (LAR) will be approached while subject is in the ICU/progressive care. If subject is unable to participate in the consenting process, the LAR will be contact via telephone and/or video chat. Consents will be sent to LAR electronically. PI and/or Sub-I will be present for all consenting process regardless is the ICF process takes place in person or video digital presence.

The randomization will be done by using *Stratified Permuted Block Randomization* in which sequential trial participants will be subdivided into the strata as indicated by their age-groups ie; 40-59, 60-74, 75-85 years and thereafter allocated to study group via block randomization within the strata so that the balance between age groups between the two study groups stays close to equal throughout the trial.

Section 5.0 Treatment Plan of Research Design:

A prospective block randomized phase I/II two arm unblinded trial of a modified SGB protocol incorporated into Standard of Care vs UNMC standard of care Only for ARDS COVID-19 patients.

Sixteen subjects will be enrolled. Eight in the control arm and eight in the intervention SGB arm.

Subjects will be identified on the COVID unit. The study will be explained to the subject and if the subject wishes to voluntarily participate, the ICF will be signed. If the subject is unable to sign consent, the LAR consent will be utilized. If LAR is not present, an electronic link to the consent will be sent to the LAR via email.

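### Randomisation is stratified by age, but no between-arm analysis is specified to include age; if age predicts the biomarker, the unadjusted tests are conservative and their intervals too wide

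*Combined protocol and SAP*

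**What the plan says.** **Randomisation (Section 4.0).** Patients are "subdivided into the strata as indicated by their age-groups ie; 40-59, 60-74, 75-85 years" and allocated by permuted blocks within stratum, "so that the balance between age groups between the two study groups stays close to equal throughout the trial". Block size is not given. Section 3.0 sets eligibility as "Subject admitted to COVID ICU/progressive care, age 40-75 years old", so only a patient aged exactly 75 can enter the top stratum.

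**Analysis (Sections 6.0 and 10.0).** Section 6.0(a) promises, at each time point, the SGB minus SOC difference with a 95% interval and a test. Section 10.0 supplies the tests: "comparisons using t test or the Mann-Whitney U test as appropriate". Section 6.0(b) compares the arms at Day 5, adjusted for baseline level. Section 10.0 also plans GEE adjusted for confounders, an ANCOVA-type regression for before-after change, and Cox regression to examine confounders. The confounders are not listed. Neither age nor the randomisation stratum is named in any analysis, and none of these analyses is ranked above the others.

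**Sample size (Section 6.0).** The plan states "we estimate the overall mean (SD) IL-6 for COVID-19 patients to be 21 pg/mL (30.1". With 8 per arm it claims power for a "magnitude of differences in mean of IL-6 from as small as about 50 pg/mL and larger with 80% power at the 5% significance level", two-sided. It takes no credit for stratification.

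**The concern.** Balancing the arms on age removes age differences from the true sampling error of the treatment contrast. A t test or Mann-Whitney test that ignores age still counts age variation as noise. If age is related to the outcome, the standard error is then overstated, p values are too large and intervals too wide. Adjusted models are planned, but without naming age. Whether the stratification factor enters is therefore left to a choice made after the data are seen.

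With 16 patients, precision is scarce. The estimates and intervals are the main product of this trial, because Section 10.0 says non-significant trends will be carried into a larger phase IIb/III trial.

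**Working it through.** **Inputs.** From Section 6.0: 8 per arm, overall SD 30.1 pg/mL, two-sided 5%, 80% power. Assumed, because the documents give no value: the share R² of outcome variance explained by age stratum; blocks of 4; two effective strata of equal expected size; normal outcomes.

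**Step 1: the plan's own figure.** The standard error of the difference is 30.1 × √(2/8) = 15.05 pg/mL.
- t test, 14 df: at 50 pg/mL the noncentrality is 50/15.05 = 3.32 and power is 87.0%. The difference detectable with 80% power is 45.3 pg/mL.
- Mann-Whitney at its lower-bound efficiency of 0.864: effective n is 8 × 0.864 = 6.91 per arm, the detectable difference is 49.5 pg/mL, and power at 50 is 80.8%.

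The second reproduces the stated figure of about 50, although the plan does not say which method it used. I use 45.3 pg/mL below, where the plain t test has 80% power.

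**Step 2: the mechanism, with two strata balanced 4/4 and 4/4.**
- True variance of the difference: (2/8) × σ²(1 − R²).
- Expected unadjusted estimate of it: (2/8) × σ²[(1 − R²) + 16R²/14].

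At R² = 0.2, σ² = 30.1² = 906.0:
- true: 0.25 × 906.0 × 0.8 = 181.2, SE 13.46;
- estimated: 0.25 × 906.0 × (0.8 + 0.2286) = 233.0, SE 15.26.

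The ratio of SEs is 1.134. Adjusting costs one degree of freedom (t quantile 2.160 on 13 df against 2.145 on 14), so the unadjusted interval is about 1.134 × 2.145/2.160 = 1.126 times as wide.

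**Step 3: simulation with strata filling at random and blocks often incomplete.** Total SD held at 30.1; 20,000 trials per setting; t test against regression on arm and stratum.

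| R² | Size, unadjusted | Power at 45.3: unadjusted / adjusted | Power at 50: unadjusted / adjusted | Interval width, unadjusted ÷ adjusted |
|---|---|---|---|---|
| 0 | 4.9% | 80% / 79% | 87% / 86% | 0.99 |
| 0.10 | 4.2% | 80% / 83% | 87% / 89% | 1.05 |
| 0.20 | 3.4% | 81% / 87% | 88% / 92% | 1.11–1.12 |
| 0.36 | 1.8% | 83% / 93% | 90% / 97% | 1.25 |

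The adjusted test stays at about 5%. With perfectly balanced strata (4/4 and 4/4), unadjusted size is 3.8% at R² = 0.1 and 2.9% at 0.2 for the t test, and 4.0% and 2.9% for Mann-Whitney.

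**The case against.** **Adjusted models are already planned.** True: GEE, ANCOVA and Cox regression stand in Section 10.0, so it would be wrong to say that the whole plan ignores age. But their covariates are unnamed and they are not made the reported comparison, so the gap remains.

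**The conservatism is conditional.** This stands. The documents give no association between age and any biomarker. If there is none, the tests hold their level and adjusting costs about 1 point of power.

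**Planned power is not lost.** This also stands. A reader might infer that the unadjusted tests miss the planned 80%. Taking 30.1 as the within-stratum SD and adding age variation on top gives unadjusted power of about 71% at R² = 0.20 and 61% at 0.36. But 30.1 is given as the overall SD, so it already contains any age variation. On that scale unadjusted power at 45.3 pg/mL stays at 80–83%.

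**The error is in the safe direction.** Correct. A reader might infer that the 95% intervals fail their coverage. They over-cover, and false positives are not inflated.

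**Incomplete blocks can restore the size.** In one assumed layout (5/3 and 3/5) unadjusted size returns to about 4.7–4.9% at R² of 0.1–0.2. That does not favour omitting age. With stratum effects of ±√0.2 × 30.1 = ±13.46, this layout shifts the unadjusted difference by 0.5 × 13.46 = 6.7 pg/mL. When the shift opposes the effect, power at 45 pg/mL is 67% unadjusted against 85% adjusted. When strata fill at random the average result is conservative, as in the table.

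**Baseline may absorb part of the age effect.** This stands for Section 6.0(b) and the ANCOVA. The simulation has no baseline covariate, so its figures apply to the unadjusted tests, and the gain from adding age to a baseline-adjusted model could be smaller.

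**Conclusion.** The point holds as a cheap improvement in specification. Age is used to stratify allocation but is not specified in any analysis. If age explains 10–20% of biomarker variance, the unadjusted tests run at a true size of about 4% to 3%, give up about 3 to 6 points of attainable power at 45.3 pg/mL, and produce intervals about 5% to 11% wider than necessary. If age explains nothing, nothing is lost by omitting it. The range rests on assumed values of R², blocks of 4, two effective strata and normal outcomes. The documents do not support a claim that the trial falls below its stated power or that its error rate is inflated. For a 16-patient phase I/II trial the consequence is modest.

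**What to change.** - State in Section 10.0 that age (randomisation stratum, or age in years) and the baseline value are fixed covariates in the ANCOVA at each time point and in the GEE, always included whatever other confounders are considered.
- Make these models the reported between-arm comparisons for Section 6.0(a) to (c).
- Where a rank test is used, stratify it by age group (van Elteren).
- For analysis, pool the 75–85 stratum with 60–74, since eligibility ends at 75 and that stratum will be nearly empty. Reconcile the age limits in Sections 3.0 and 4.0.

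Cost: a few sentences of SAP text, no new data, one degree of freedom, and about 1 point of power if age is unrelated to the outcome.

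### The GEE slope comparison has 16 patients and no stated small-sample method; with uncorrected sandwich errors and a z test, a nominal 5% test would reject about 8.8% under no effect for normal data and about 6-8% for skewed data

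*Combined protocol and SAP*

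**What the plan says.** - **Model.** Section 10.0 lists, for the primary objective, "Multivariate analyses using Generalized estimating equations (GEE) and to compare longitudinal changes in the two groups adjusting for confounders", alongside t or Mann-Whitney tests at each time point and ANCOVA. It names no working correlation, standard error type, z or t reference, small-sample correction or outcome transformation. The confounders are not named.
- **Quantity.** Section 6.0(c): "Differences in changes from baseline levels for SGB vs SOC as measured by comparison in slope trends". Section 6.0(b) separately plans the comparison that adjusts for baseline: "Differences in mean/median values for SGB vs SOC will be assessed at treatment day 5 - adjusted for baseline levels".
- **Size.** Section 5.0: "Sixteen subjects will be enrolled. Eight in the control arm and eight in the intervention SGB arm".
- **Sampling.** Section 5.0: "Laboratory analysis will be obtained at baseline (prior to block, baseline) and on day 1, day 3, and day 5". CRP and nitric oxide are daily in the schedule of events.
- **Early ends.** Section 9.0: "For continuous infusions, the catheter will be removed and the patient will be withdrawn if any of the following occur". The plan does not say whether sampling continues after withdrawal.
- **Stratification.** Section 4.0 has randomised patients "subdivided into the strata as indicated by their age-groups ie; 40-59, 60-74, 75-85 years". No analysis names this stratum. Section 3.0 admits: "Subject admitted to COVID ICU/progressive care, age 40-75 years old"; the Brief Summary gives the same limits.

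**The concern.** Sandwich standard errors rely on a large number of clusters. Here the clusters are patients, and there are 16. Without a correction, the estimator understates the variance of the slope difference, and a z reference ignores that the variance is itself estimated. Both push the p value down and narrow the interval.

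The slope results across IL-6, TNF, IL-1 beta, CRP and nitric oxide are part of what a later phase IIb/III trial would build on, so overstated precision would carry forward. Because the trial is unblinded and the estimator is not fixed, the choice could also be made after the data are seen, and the options give different error rates on the same data.

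**Working it through.** **Plan's own figure.** The plan states no error rate for the GEE. Its only power figure (Section 6.0) is 80% at an IL-6 difference of about 50 pg/mL, SD 30.1, 8 per arm, two-sided 5%. A t test gives 87.0% at 50 and 80% at 45.3. The stated value is conservative and approximate; it is not treated as an error and does not bear on this point.

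**Inputs from the plan.** 8 per arm; days 0, 1, 3, 5 for cytokines and days 0-5 for CRP and nitric oxide; IL-6 mean 21, SD 30.1. The two-sided 5% level is taken from the power statement.

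**Closed form (complete normal data).** With an independence or exchangeable working correlation and identity link, the GEE slope difference equals the difference in mean per-patient least-squares slopes. The uncorrected sandwich variance divides by n = 8 where the t test divides by n - 1 = 7, so its standard error is the t-test standard error times √(7/8). Mancl-DeRouen multiplies the t-test standard error by √(8/7). The 5% critical value of t with 14 df is 2.145.

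| Method | Equivalent event | Null rejection |
|---|---|---|
| Uncorrected sandwich, z | \|t14\| > 1.96 × √(7/8) = 1.833 | 8.8% |
| Uncorrected sandwich, t(14) | \|t14\| > 2.145 × √(7/8) = 2.006 | 6.5% |
| Per-patient slope t test | \|t14\| > 2.145 | 5.0% |
| Mancl-DeRouen, t(14) | \|t14\| > 2.145 × √(8/7) = 2.293 | 3.8% |

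These values depend only on 8 per arm, so they hold for both sampling schedules. With fewer evaluable patients, the first row becomes 9.5% for 7 per arm (\|t12\| > 1.96 × √(6/7)) and 10.4% for 6 per arm (\|t10\| > 1.96 × √(5/6)). A standard GEE routine with its default robust errors and an exchangeable correlation rejected 8.9% in 8,000 simulated null trials.

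**Skewed data.** The IL-6 coefficient of variation is 30.1/21 = 1.43; a lognormal with that value has log-SD √ln(1 + 1.43²) = 1.057. Assumed within-patient correlation was 0.3-0.8 across the simulations.
- Uncorrected z: 6.2-7.8%, falling to 5.5-6.3% with a heavier skew (log-SD 1.5).
- Slope t test: 2.5-3.6%.
- Mancl-DeRouen with t: 1.7-2.6%.

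**Series cut short (assumption: 2 of 8 per arm, half after day 1 and half after day 3, unrelated to outcome).**
- Uncorrected z: 9.9-10.3% (normal) and 6.7-7.9% (lognormal).
- Mancl-DeRouen with t: 4.2-4.8% and 1.7-2.6%.

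**Interval width relative to uncorrected z.** Slope t test: √(8/7) × 2.145/1.96 = 1.17. Mancl-DeRouen with t: (8/7) × 2.145/1.96 = 1.25.

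**Power (assumed correlation 0.5, no random slope, normal, difference 0.28 SD per day).** For days 0, 1, 3, 5 the sum of squares about the mean day is 14.75. The slope SD is √(0.5/14.75) = 0.184, the standard error of the difference is 0.184 × √(2/8) = 0.092, and the noncentrality is 0.28/0.092 = 3.04.
- Complete data: about 81% for the slope t test and 77% for Mancl-DeRouen with t (80% and 76% by simulation).
- One series lacking only day 5: 77% and 76%; with a random-slope SD of 0.15, 58% and 53%.
- Two of 8 series per arm cut short as above, so that some end after day 1: 35% and 66%.

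**The case against.** The strongest reply is that this is conditional and small. The plan does not say that uncorrected errors with z will be used. IL-6 with mean 21 and SD 30.1 is not plausibly normal, and at that skew the excess over 5% is roughly 1 to 3 points. The trial is a phase I/II proof of concept, GEE is one of several analyses for the primary objective, many biomarkers are tested at every time point without a multiplicity rule, and no stopping rule uses a slope p value. All of this stands and sets the weight of the point. It does not remove it, because the remedy is a sentence.

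Four technical limits also stand:
- **Working correlation.** The equality of the two estimates needs an independence or exchangeable structure. With AR(1) 0.7 over daily days 0-5, the first and last days get weights of -0.188 and 0.188 instead of -0.143 and 0.143. The two slope estimates then correlate at about 0.97 but are not identical.
- **Confounders.** A reader might infer that unnamed confounders inflate the slope test further. With complete data, patient-level main effects change neither the slope difference nor its standard error. Time-varying covariates could matter slightly: adding two binary ones gave 9.8% against 8.9% in one simulation.
- **Missing samples.** A reader might infer that any incomplete series calls for the corrected GEE. The power figures do not support that: with a single missed day 5 the slope t test is no worse. The large loss appears when series end after day 1.
- **Age stratum.** The confounders could already include age. A gain of 71% to 79% in power needs an assumed 1 SD difference in slope between strata; with no age effect, power is 79.5% without the stratum and 78.9% with it.

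**Conclusion.** The plan leaves the small-sample method for its slope comparison unspecified with 16 patients. Under the usual uncorrected sandwich and z test, a nominal 5% test would reject 8.8% for complete normal data and about 6-8% at the plan's IL-6 skew. The 8.8% rests only on normality, complete data, 8 per arm and an independence or exchangeable working correlation with identity link. The other figures rest on assumed correlation, skew and dropout. Neither end is a bound: very heavy skew brings the rate to 5.5%, and early ends or fewer patients take it to about 10%.

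A reader might infer that the trial has a false-positive rate near 9%. The documents do not support that: the estimator is left open, and this is one analysis among several. It is a worthwhile, inexpensive correction, and it does not by itself invalidate the trial.

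Two related gaps hold. The stratum used in randomisation is named in no analysis. The 75-85 stratum also disagrees with the 40-75 age limit; this is a separate inconsistency and adds no weight to the point about standard errors.

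**What to change.** 1. **Fix one method in advance, with no switch triggered by a single missing sample.** Either:
   - GEE with an independence or exchangeable working correlation, Mancl-DeRouen standard errors and a t reference (14 df, less any patient-level slope terms); or
   - a two-sample t test on per-patient slopes as the main analysis, with the corrected GEE as a sensitivity analysis when series end early.
2. **Include the randomisation age stratum** in the between-arm models. In the GEE slope model it must enter as stratum-by-day to adjust the slope; in the per-patient slope analysis it is a factor in the regression. Age 75 is eligible, so the third stratum can be filled.
3. **Keep the baseline biomarker as a covariate in the day 5 comparison** of Section 6.0(b). In the slope model, day 0 is a response.
4. **Separately, reconcile the strata** in Section 4.0 with the age limits in Section 3.0 and the Brief Summary.

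**Cost.** SAP wording and one software option. With complete data, an independence or exchangeable working correlation and an identity link, the two options give the same slope difference. Intervals widen 1.17-fold (slope t test) or 1.25-fold (Mancl-DeRouen with t). Mancl-DeRouen is conservative for skewed data, at about 2-3%. The stratum costs one df for each filled stratum beyond the first: 13 df with two, 12 with three.
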